10.8 Appendix 8: Dosing tables

Procedure to find the correct dose

A pen strength of 15 mg/1.5 mL will be used in this study. The dose table covers a body weight range from 9 to 125 kg. Use the dose table ([Table 10-8](#)) to find the precise dose using the participant's current weight. In case of dose reduction, dosing tables will be provided by Novo Nordisk.

Information to participant's parents/LAR regarding dose

Participant's parents/LAR must be informed about the prescribed dose to be administered. Instruct the participant's parents/LAR on how to select the prescribed dose on the pen injector.

Splitting the dose

A dose may be split into equal administrations in case the dose is higher than the pen can dispense for one administration. If a dose is split, it should be injected into the same body location.

Table 10-8 Dose table for 0.24 mg/kg somapacitan – 15 mg/1.5 mL strength

Somapacitan 15mg/1.5ml - Dose Level 0.24mg/kg								
Weight (kg)		Weight (lb)		Dosing				
Start	End	Start	End	Total Dose	Dose 1	Dose 2	Dose 3	Dose 4
9.0	9.3	19.8	20.6	2.2	2.2	0.0	0.0	0.0
9.4	9.7	20.7	21.5	2.3	2.3	0.0	0.0	0.0
9.8	10.1	21.6	22.4	2.4	2.4	0.0	0.0	0.0
10.2	10.6	22.5	23.5	2.5	2.5	0.0	0.0	0.0
10.7	11.0	23.6	24.4	2.6	2.6	0.0	0.0	0.0
11.1	11.4	24.5	25.3	2.7	2.7	0.0	0.0	0.0
11.5	11.8	25.4	26.1	2.8	2.8	0.0	0.0	0.0
11.9	12.2	26.2	27.0	2.9	2.9	0.0	0.0	0.0
12.3	12.6	27.1	27.9	3.0	3.0	0.0	0.0	0.0
12.7	13.1	28.0	29.0	3.1	3.1	0.0	0.0	0.0
13.2	13.5	29.1	29.9	3.2	3.2	0.0	0.0	0.0
13.6	13.9	30.0	30.8	3.3	3.3	0.0	0.0	0.0
14.0	14.3	30.9	31.6	3.4	3.4	0.0	0.0	0.0
14.4	14.7	31.7	32.5	3.5	3.5	0.0	0.0	0.0
14.8	15.1	32.6	33.4	3.6	3.6	0.0	0.0	0.0
15.2	15.6	33.5	34.5	3.7	3.7	0.0	0.0	0.0
15.7	16.0	34.6	35.4	3.8	3.8	0.0	0.0	0.0
16.1	16.4	35.5	36.3	3.9	3.9	0.0	0.0	0.0
16.5	16.8	36.4	37.2	4.0	4.0	0.0	0.0	0.0
16.9	17.2	37.3	38.0	4.1	4.1	0.0	0.0	0.0
17.3	17.6	38.1	38.9	4.2	4.2	0.0	0.0	0.0
17.7	18.1	39.0	40.0	4.3	4.3	0.0	0.0	0.0
18.2	18.5	40.1	40.9	4.4	4.4	0.0	0.0	0.0
18.6	18.9	41.0	41.8	4.5	4.5	0.0	0.0	0.0
19.0	19.3	41.9	42.7	4.6	4.6	0.0	0.0	0.0
19.4	19.7	42.8	43.6	4.7	4.7	0.0	0.0	0.0
19.8	20.1	43.7	44.4	4.8	4.8	0.0	0.0	0.0
20.2	20.6	44.5	45.5	4.9	4.9	0.0	0.0	0.0
20.7	21.0	45.6	46.4	5.0	5.0	0.0	0.0	0.0

Somapacitan 15mg/1.5ml - Dose Level 0.24mg/kg								
Weight (kg)		Weight (lb)		Dosing				
Start	End	Start	End	Total Dose	Dose 1	Dose 2	Dose 3	Dose 4
21.1	21.4	46.5	47.3	5.1	5.1	0.0	0.0	0.0
21.5	21.8	47.4	48.2	5.2	5.2	0.0	0.0	0.0
21.9	22.2	48.3	49.1	5.3	5.3	0.0	0.0	0.0
22.3	22.6	49.2	49.9	5.4	5.4	0.0	0.0	0.0
22.7	23.1	50.0	51.0	5.5	5.5	0.0	0.0	0.0
23.2	23.5	51.1	51.9	5.6	5.6	0.0	0.0	0.0
23.6	23.9	52.0	52.8	5.7	5.7	0.0	0.0	0.0
24.0	24.3	52.9	53.7	5.8	5.8	0.0	0.0	0.0
24.4	24.7	53.8	54.6	5.9	5.9	0.0	0.0	0.0
24.8	25.1	54.7	55.5	6.0	6.0	0.0	0.0	0.0
25.2	25.6	55.6	56.6	6.1	6.1	0.0	0.0	0.0
25.7	26.0	56.7	57.4	6.2	6.2	0.0	0.0	0.0
26.1	26.4	57.5	58.3	6.3	6.3	0.0	0.0	0.0
26.5	26.8	58.4	59.2	6.4	6.4	0.0	0.0	0.0
26.9	27.2	59.3	60.1	6.5	6.5	0.0	0.0	0.0
27.3	27.6	60.2	61.0	6.6	6.6	0.0	0.0	0.0
27.7	28.1	61.1	62.1	6.7	6.7	0.0	0.0	0.0
28.2	28.5	62.2	63.0	6.8	6.8	0.0	0.0	0.0
28.6	28.9	63.1	63.8	6.9	6.9	0.0	0.0	0.0
29.0	29.3	63.9	64.7	7.0	7.0	0.0	0.0	0.0
29.4	29.7	64.8	65.6	7.1	7.1	0.0	0.0	0.0
29.8	30.1	65.7	66.5	7.2	7.2	0.0	0.0	0.0
30.2	30.6	66.6	67.6	7.3	7.3	0.0	0.0	0.0
30.7	31.0	67.7	68.5	7.4	7.4	0.0	0.0	0.0
31.1	31.4	68.6	69.3	7.5	7.5	0.0	0.0	0.0
31.5	31.8	69.4	70.2	7.6	7.6	0.0	0.0	0.0
31.9	32.2	70.3	71.1	7.7	7.7	0.0	0.0	0.0
32.3	32.6	71.2	72.0	7.8	7.8	0.0	0.0	0.0
32.7	33.1	72.1	73.1	7.9	7.9	0.0	0.0	0.0
33.2	33.5	73.2	74.0	8.0	8.0	0.0	0.0	0.0
33.6	33.9	74.1	74.9	8.1	4.1	4.0	0.0	0.0
34.0	34.3	75.0	75.7	8.2	4.1	4.1	0.0	0.0
34.4	34.7	75.8	76.6	8.3	4.2	4.1	0.0	0.0
34.8	35.1	76.7	77.5	8.4	4.2	4.2	0.0	0.0
35.2	35.6	77.6	78.6	8.5	4.3	4.2	0.0	0.0
35.7	36.0	78.7	79.5	8.6	4.3	4.3	0.0	0.0
36.1	36.4	79.6	80.4	8.7	4.4	4.3	0.0	0.0
36.5	36.8	80.5	81.2	8.8	4.4	4.4	0.0	0.0
36.9	37.2	81.3	82.1	8.9	4.5	4.4	0.0	0.0
37.3	37.6	82.2	83.0	9.0	4.5	4.5	0.0	0.0
37.7	38.1	83.1	84.1	9.1	4.6	4.5	0.0	0.0
38.2	38.5	84.2	85.0	9.2	4.6	4.6	0.0	0.0
38.6	38.9	85.1	85.9	9.3	4.7	4.6	0.0	0.0
39.0	39.3	86.0	86.8	9.4	4.7	4.7	0.0	0.0
39.4	39.7	86.9	87.6	9.5	4.8	4.7	0.0	0.0
39.8	40.1	87.7	88.5	9.6	4.8	4.8	0.0	0.0
40.2	40.6	88.6	89.6	9.7	4.9	4.8	0.0	0.0
40.7	41.0	89.7	90.5	9.8	4.9	4.9	0.0	0.0
41.1	41.4	90.6	91.4	9.9	5.0	4.9	0.0	0.0

Somapacitan 15mg/1.5ml - Dose Level 0.24mg/kg								
Weight (kg)		Weight (lb)		Dosing				
Start	End	Start	End	Total Dose	Dose 1	Dose 2	Dose 3	Dose 4
41.5	41.8	91.5	92.3	10.0	5.0	5.0	0.0	0.0
41.9	42.2	92.4	93.2	10.1	5.1	5.0	0.0	0.0
42.3	42.6	93.3	94.0	10.2	5.1	5.1	0.0	0.0
42.7	43.1	94.1	95.1	10.3	5.2	5.1	0.0	0.0
43.2	43.5	95.2	96.0	10.4	5.2	5.2	0.0	0.0
43.6	43.9	96.1	96.9	10.5	5.3	5.2	0.0	0.0
44.0	44.3	97.0	97.8	10.6	5.3	5.3	0.0	0.0
44.4	44.7	97.9	98.7	10.7	5.4	5.3	0.0	0.0
44.8	45.1	98.8	99.5	10.8	5.4	5.4	0.0	0.0
45.2	45.6	99.6	100.7	10.9	5.5	5.4	0.0	0.0
45.7	46.0	100.8	101.5	11.0	5.5	5.5	0.0	0.0
46.1	46.4	101.6	102.4	11.1	5.6	5.5	0.0	0.0
46.5	46.8	102.5	103.3	11.2	5.6	5.6	0.0	0.0
46.9	47.2	103.4	104.2	11.3	5.7	5.6	0.0	0.0
47.3	47.6	104.3	105.1	11.4	5.7	5.7	0.0	0.0
47.7	48.1	105.2	106.2	11.5	5.8	5.7	0.0	0.0
48.2	48.5	106.3	107.0	11.6	5.8	5.8	0.0	0.0
48.6	48.9	107.1	107.9	11.7	5.9	5.8	0.0	0.0
49.0	49.3	108.0	108.8	11.8	5.9	5.9	0.0	0.0
49.4	49.7	108.9	109.7	11.9	6.0	5.9	0.0	0.0
49.8	50.1	109.8	110.6	12.0	6.0	6.0	0.0	0.0
50.2	50.6	110.7	111.7	12.1	6.1	6.0	0.0	0.0
50.7	51.0	111.8	112.6	12.2	6.1	6.1	0.0	0.0
51.1	51.4	112.7	113.4	12.3	6.2	6.1	0.0	0.0
51.5	51.8	113.5	114.3	12.4	6.2	6.2	0.0	0.0
51.9	52.2	114.4	115.2	12.5	6.3	6.2	0.0	0.0
52.3	52.6	115.3	116.1	12.6	6.3	6.3	0.0	0.0
52.7	53.1	116.2	117.2	12.7	6.4	6.3	0.0	0.0
53.2	53.5	117.3	118.1	12.8	6.4	6.4	0.0	0.0
53.6	53.9	118.2	118.9	12.9	6.5	6.4	0.0	0.0
54.0	54.3	119.0	119.8	13.0	6.5	6.5	0.0	0.0
54.4	54.7	119.9	120.7	13.1	6.6	6.5	0.0	0.0
54.8	55.1	120.8	121.6	13.2	6.6	6.6	0.0	0.0
55.2	55.6	121.7	122.7	13.3	6.7	6.6	0.0	0.0
55.7	56.0	122.8	123.6	13.4	6.7	6.7	0.0	0.0
56.1	56.4	123.7	124.5	13.5	6.8	6.7	0.0	0.0
56.5	56.8	124.6	125.3	13.6	6.8	6.8	0.0	0.0
56.9	57.2	125.4	126.2	13.7	6.9	6.8	0.0	0.0
57.3	57.6	126.3	127.1	13.8	6.9	6.9	0.0	0.0
57.7	58.1	127.2	128.2	13.9	7.0	6.9	0.0	0.0
58.2	58.5	128.3	129.1	14.0	7.0	7.0	0.0	0.0
58.6	58.9	129.2	130.0	14.1	7.1	7.0	0.0	0.0
59.0	59.3	130.1	130.9	14.2	7.1	7.1	0.0	0.0
59.4	59.7	131.0	131.7	14.3	7.2	7.1	0.0	0.0
59.8	60.1	131.8	132.6	14.4	7.2	7.2	0.0	0.0
60.2	60.6	132.7	133.7	14.5	7.3	7.2	0.0	0.0
60.7	61.0	133.8	134.6	14.6	7.3	7.3	0.0	0.0
61.1	61.4	134.7	135.5	14.7	7.4	7.3	0.0	0.0
61.5	61.8	135.6	136.4	14.8	7.4	7.4	0.0	0.0

Somapacitan 15mg/1.5ml - Dose Level 0.24mg/kg									
Weight (kg)		Weight (lb)		Dosing					
Start	End	Start	End	Total Dose	Dose 1	Dose 2	Dose 3	Dose 4	
61.9	62.2	136.5	137.2	14.9	7.5	7.4	0.0	0.0	
62.3	62.6	137.3	138.1	15.0	7.5	7.5	0.0	0.0	
62.7	63.1	138.2	139.2	15.1	7.6	7.5	0.0	0.0	
63.2	63.5	139.3	140.1	15.2	7.6	7.6	0.0	0.0	
63.6	63.9	140.2	141.0	15.3	7.7	7.6	0.0	0.0	
64.0	64.3	141.1	141.9	15.4	7.7	7.7	0.0	0.0	
64.4	64.7	142.0	142.8	15.5	7.8	7.7	0.0	0.0	
64.8	65.1	142.9	143.6	15.6	7.8	7.8	0.0	0.0	
65.2	65.6	143.7	144.7	15.7	7.9	7.8	0.0	0.0	
65.7	66.0	144.8	145.6	15.8	7.9	7.9	0.0	0.0	
66.1	66.4	145.7	146.5	15.9	8.0	7.9	0.0	0.0	
66.5	66.8	146.6	147.4	16.0	8.0	8.0	0.0	0.0	
66.9	67.2	147.5	148.3	16.1	5.4	5.4	5.3	0.0	
67.3	67.6	148.4	149.2	16.2	5.4	5.4	5.4	0.0	
67.7	68.1	149.3	150.3	16.3	5.4	5.4	5.5	0.0	
68.2	68.5	150.4	151.1	16.4	5.5	5.5	5.4	0.0	
68.6	68.9	151.2	152.0	16.5	5.5	5.5	5.5	0.0	
69.0	69.3	152.1	152.9	16.6	5.5	5.5	5.6	0.0	
69.4	69.7	153.0	153.8	16.7	5.6	5.6	5.5	0.0	
69.8	70.1	153.9	154.7	16.8	5.6	5.6	5.6	0.0	
70.2	70.6	154.8	155.8	16.9	5.6	5.6	5.7	0.0	
70.7	71.0	155.9	156.6	17.0	5.7	5.7	5.6	0.0	
71.1	71.4	156.7	157.5	17.1	5.7	5.7	5.7	0.0	
71.5	71.8	157.6	158.4	17.2	5.7	5.7	5.8	0.0	
71.9	72.2	158.5	159.3	17.3	5.8	5.8	5.7	0.0	
72.3	72.6	159.4	160.2	17.4	5.8	5.8	5.8	0.0	
72.7	73.1	160.3	161.3	17.5	5.8	5.8	5.9	0.0	
73.2	73.5	161.4	162.2	17.6	5.9	5.9	5.8	0.0	
73.6	73.9	162.3	163.0	17.7	5.9	5.9	5.9	0.0	
74.0	74.3	163.1	163.9	17.8	5.9	5.9	6.0	0.0	
74.4	74.7	164.0	164.8	17.9	6.0	6.0	5.9	0.0	
74.8	75.1	164.9	165.7	18.0	6.0	6.0	6.0	0.0	
75.2	75.6	165.8	166.8	18.1	6.0	6.0	6.1	0.0	
75.7	76.0	166.9	167.7	18.2	6.1	6.1	6.0	0.0	
76.1	76.4	167.8	168.6	18.3	6.1	6.1	6.1	0.0	
76.5	76.8	168.7	169.4	18.4	6.1	6.1	6.2	0.0	
76.9	77.2	169.5	170.3	18.5	6.2	6.2	6.1	0.0	
77.3	77.6	170.4	171.2	18.6	6.2	6.2	6.2	0.0	
77.7	78.1	171.3	172.3	18.7	6.2	6.2	6.3	0.0	
78.2	78.5	172.4	173.2	18.8	6.3	6.3	6.2	0.0	
78.6	78.9	173.3	174.1	18.9	6.3	6.3	6.3	0.0	
79.0	79.3	174.2	174.9	19.0	6.3	6.3	6.4	0.0	
79.4	79.7	175.0	175.8	19.1	6.4	6.4	6.3	0.0	
79.8	80.1	175.9	176.7	19.2	6.4	6.4	6.4	0.0	
80.2	80.6	176.8	177.8	19.3	6.4	6.4	6.5	0.0	
80.7	81.0	177.9	178.7	19.4	6.5	6.5	6.4	0.0	
81.1	81.4	178.8	179.6	19.5	6.5	6.5	6.5	0.0	
81.5	81.8	179.7	180.5	19.6	6.5	6.5	6.6	0.0	
81.9	82.2	180.6	181.3	19.7	6.6	6.6	6.5	0.0	

Somapacitan 15mg/1.5ml - Dose Level 0.24mg/kg								
Weight (kg)		Weight (lb)		Dosing				
Start	End	Start	End	Total Dose	Dose 1	Dose 2	Dose 3	Dose 4
82.3	82.6	181.4	182.2	19.8	6.6	6.6	6.6	0.0
82.7	83.1	182.3	183.3	19.9	6.6	6.6	6.7	0.0
83.2	83.5	183.4	184.2	20.0	6.7	6.7	6.6	0.0
83.6	83.9	184.3	185.1	20.1	6.7	6.7	6.7	0.0
84.0	84.3	185.2	186.0	20.2	6.7	6.7	6.8	0.0
84.4	84.7	186.1	186.9	20.3	6.8	6.8	6.7	0.0
84.8	85.1	187.0	187.7	20.4	6.8	6.8	6.8	0.0
85.2	85.6	187.8	188.8	20.5	6.8	6.8	6.9	0.0
85.7	86.0	188.9	189.7	20.6	6.9	6.9	6.8	0.0
86.1	86.4	189.8	190.6	20.7	6.9	6.9	6.9	0.0
86.5	86.8	190.7	191.5	20.8	6.9	6.9	7.0	0.0
86.9	87.2	191.6	192.4	20.9	7.0	7.0	6.9	0.0
87.3	87.6	192.5	193.2	21.0	7.0	7.0	7.0	0.0
87.7	88.1	193.3	194.3	21.1	7.0	7.0	7.1	0.0
88.2	88.5	194.4	195.2	21.2	7.1	7.1	7.0	0.0
88.6	88.9	195.3	196.1	21.3	7.1	7.1	7.1	0.0
89.0	89.3	196.2	197.0	21.4	7.1	7.1	7.2	0.0
89.4	89.7	197.1	197.9	21.5	7.2	7.2	7.1	0.0
89.8	90.1	198.0	198.8	21.6	7.2	7.2	7.2	0.0
90.2	90.6	198.9	199.9	21.7	7.2	7.2	7.3	0.0
90.7	91.0	200.0	200.7	21.8	7.3	7.3	7.2	0.0
91.1	91.4	200.8	201.6	21.9	7.3	7.3	7.3	0.0
91.5	91.8	201.7	202.5	22.0	7.3	7.3	7.4	0.0
91.9	92.2	202.6	203.4	22.1	7.4	7.4	7.3	0.0
92.3	92.6	203.5	204.3	22.2	7.4	7.4	7.4	0.0
92.7	93.1	204.4	205.4	22.3	7.4	7.4	7.5	0.0
93.2	93.5	205.5	206.3	22.4	7.5	7.5	7.4	0.0
93.6	93.9	206.4	207.1	22.5	7.5	7.5	7.5	0.0
94.0	94.3	207.2	208.0	22.6	7.5	7.5	7.6	0.0
94.4	94.7	208.1	208.9	22.7	7.6	7.6	7.5	0.0
94.8	95.1	209.0	209.8	22.8	7.6	7.6	7.6	0.0
95.2	95.6	209.9	210.9	22.9	7.6	7.6	7.7	0.0
95.7	96.0	211.0	211.8	23.0	7.7	7.7	7.6	0.0
96.1	96.4	211.9	212.6	23.1	7.7	7.7	7.7	0.0
96.5	96.8	212.7	213.5	23.2	7.7	7.7	7.8	0.0
96.9	97.2	213.6	214.4	23.3	7.8	7.8	7.7	0.0
97.3	97.6	214.5	215.3	23.4	7.8	7.8	7.8	0.0
97.7	98.1	215.4	216.4	23.5	7.8	7.8	7.9	0.0
98.2	98.5	216.5	217.3	23.6	7.9	7.9	7.8	0.0
98.6	98.9	217.4	218.2	23.7	7.9	7.9	7.9	0.0
99.0	99.3	218.3	219.0	23.8	7.9	7.9	8.0	0.0
99.4	99.7	219.1	219.9	23.9	8.0	8.0	7.9	0.0
99.8	100.1	220.0	220.8	24.0	8.0	8.0	8.0	0.0
100.2	100.6	220.9	221.9	24.1	6.0	6.0	6.0	6.1
100.7	101.0	222.0	222.8	24.2	6.1	6.1	6.1	5.9
101.1	101.4	222.9	223.7	24.3	6.1	6.1	6.1	6.0
101.5	101.8	223.8	224.5	24.4	6.1	6.1	6.1	6.1
101.9	102.2	224.6	225.4	24.5	6.1	6.1	6.1	6.2
102.3	102.6	225.5	226.3	24.6	6.2	6.2	6.2	6.0

Somapacitan 15mg/1.5ml - Dose Level 0.24mg/kg								
Weight (kg)		Weight (lb)		Dosing				
Start	End	Start	End	Total Dose	Dose 1	Dose 2	Dose 3	Dose 4
102.7	103.1	226.4	227.4	24.7	6.2	6.2	6.2	6.1
103.2	103.5	227.5	228.3	24.8	6.2	6.2	6.2	6.2
103.6	103.9	228.4	229.2	24.9	6.2	6.2	6.2	6.3
104.0	104.3	229.3	230.1	25.0	6.3	6.3	6.3	6.1
104.4	104.7	230.2	230.9	25.1	6.3	6.3	6.3	6.2
104.8	105.1	231.0	231.8	25.2	6.3	6.3	6.3	6.3
105.2	105.6	231.9	232.9	25.3	6.3	6.3	6.3	6.4
105.7	106.0	233.0	233.8	25.4	6.4	6.4	6.4	6.2
106.1	106.4	233.9	234.7	25.5	6.4	6.4	6.4	6.3
106.5	106.8	234.8	235.6	25.6	6.4	6.4	6.4	6.4
106.9	107.2	235.7	236.5	25.7	6.4	6.4	6.4	6.5
107.3	107.6	236.6	237.3	25.8	6.5	6.5	6.5	6.3
107.7	108.1	237.4	238.4	25.9	6.5	6.5	6.5	6.4
108.2	108.5	238.5	239.3	26.0	6.5	6.5	6.5	6.5
108.6	108.9	239.4	240.2	26.1	6.5	6.5	6.5	6.6
109.0	109.3	240.3	241.1	26.2	6.6	6.6	6.6	6.4
109.4	109.7	241.2	242.0	26.3	6.6	6.6	6.6	6.5
109.8	110.1	242.1	242.8	26.4	6.6	6.6	6.6	6.6
110.2	110.6	242.9	243.9	26.5	6.6	6.6	6.6	6.7
110.7	111.0	244.0	244.8	26.6	6.7	6.7	6.7	6.5
111.1	111.4	244.9	245.7	26.7	6.7	6.7	6.7	6.6
111.5	111.8	245.8	246.6	26.8	6.7	6.7	6.7	6.7
111.9	112.2	246.7	247.5	26.9	6.7	6.7	6.7	6.8
112.3	112.6	247.6	248.4	27.0	6.8	6.8	6.8	6.6
112.7	113.1	248.5	249.5	27.1	6.8	6.8	6.8	6.7
113.2	113.5	249.6	250.3	27.2	6.8	6.8	6.8	6.8
113.6	113.9	250.4	251.2	27.3	6.8	6.8	6.8	6.9
114.0	114.3	251.3	252.1	27.4	6.9	6.9	6.9	6.7
114.4	114.7	252.2	253.0	27.5	6.9	6.9	6.9	6.8
114.8	115.1	253.1	253.9	27.6	6.9	6.9	6.9	6.9
115.2	115.6	254.0	255.0	27.7	6.9	6.9	6.9	7.0
115.7	116.0	255.1	255.9	27.8	7.0	7.0	7.0	6.8
116.1	116.4	256.0	256.7	27.9	7.0	7.0	7.0	6.9
116.5	116.8	256.8	257.6	28.0	7.0	7.0	7.0	7.0
116.9	117.2	257.7	258.5	28.1	7.0	7.0	7.0	7.1
117.3	117.6	258.6	259.4	28.2	7.1	7.1	7.1	6.9
117.7	118.1	259.5	260.5	28.3	7.1	7.1	7.1	7.0
118.2	118.5	260.6	261.4	28.4	7.1	7.1	7.1	7.1
118.6	118.9	261.5	262.2	28.5	7.1	7.1	7.1	7.2
119.0	119.3	262.3	263.1	28.6	7.2	7.2	7.2	7.0
119.4	119.7	263.2	264.0	28.7	7.2	7.2	7.2	7.1
119.8	120.1	264.1	264.9	28.8	7.2	7.2	7.2	7.2
120.2	120.6	265.0	266.0	28.9	7.2	7.2	7.2	7.3
120.7	121.0	266.1	266.9	29.0	7.3	7.3	7.3	7.1
121.1	121.4	267.0	267.8	29.1	7.3	7.3	7.3	7.2
121.5	121.8	267.9	268.6	29.2	7.3	7.3	7.3	7.3
121.9	122.2	268.7	269.5	29.3	7.3	7.3	7.3	7.4
122.3	122.6	269.6	270.4	29.4	7.4	7.4	7.4	7.2
122.7	123.1	270.5	271.5	29.5	7.4	7.4	7.4	7.3

Somapacitan 15mg/1.5ml - Dose Level 0.24mg/kg								
Weight (kg)		Weight (lb)		Dosing				
Start	End	Start	End	Total Dose	Dose 1	Dose 2	Dose 3	Dose 4
123.2	123.5	271.6	272.4	29.6	7.4	7.4	7.4	7.4
123.6	123.9	272.5	273.3	29.7	7.4	7.4	7.4	7.5
124.0	124.3	273.4	274.2	29.8	7.5	7.5	7.5	7.3
124.4	124.7	274.3	275.0	29.9	7.5	7.5	7.5	7.4
124.8	125.0	275.1	275.7	30.0	7.5	7.5	7.5	7.5

Dose calculation (somapacitan)

This information is only to be used for dose reduction of somapacitan.

Use the tables below ([Table 10-9](#), 0.21 mg/kg/week or [Table 10-10](#), 0.18 mg/kg/week) to find the required dose level and the participant's current weight.

Information to participant's parents/LARs regarding dose

Participant's parents/LARs must be informed about the prescribed dose and instructed in how to select the prescribed dose on the pen injector to be able to inject at home.

Splitting the dose

A dose may be split into two equal administrations in case the dose is higher than the pen can dispense for the administration. If a dose is split, it should be injected into the same body location.

Table 10-9 Selection of somapacitan dose in mg in case of dose reduction to a dose level of 0.21mg/kg

Somapacitan 15mg/1.5ml - Dose Level 0.21mg/kg				
Weight (kg)		Weight (lb)		
Start	End	Start	End	Dose
11.0	11.1	24.3	24.6	2.30
11.2	11.6	24.7	25.7	2.40
11.7	12.1	25.8	26.8	2.50
12.2	12.5	26.9	27.7	2.60
12.6	13.0	27.8	28.8	2.70
13.1	13.5	28.9	29.9	2.80
13.6	14.0	30.0	31.0	2.90
14.1	14.4	31.1	31.9	3.00
14.5	14.9	32.0	33.0	3.10
15.0	15.4	33.1	34.1	3.20
15.5	15.9	34.2	35.2	3.30
16.0	16.4	35.3	36.3	3.40
16.5	16.8	36.4	37.2	3.50
16.9	17.3	37.3	38.3	3.60

Somapacitan 15mg/1.5ml - Dose Level 0.21mg/kg				
17.4	17.8	38.4	39.4	3.70
Weight (kg)		Weight (lb)		
Start	End	Start	End	Dose
17.9	18.3	39.5	40.5	3.80
18.4	18.7	40.6	41.3	3.90
18.8	19.2	41.4	42.4	4.00
19.3	19.7	42.5	43.6	4.10
19.8	20.2	43.7	44.7	4.20
20.3	20.6	44.8	45.5	4.30
20.7	21.1	45.6	46.6	4.40
21.2	21.6	46.7	47.7	4.50
21.7	22.1	47.8	48.8	4.60
22.2	22.5	48.9	49.7	4.70
22.6	23.0	49.8	50.8	4.80
23.1	23.5	50.9	51.9	4.90
23.6	24.0	52.0	53.0	5.00
24.1	24.4	53.1	53.9	5.10
24.5	24.9	54.0	55.0	5.20
25.0	25.4	55.1	56.1	5.30
25.5	25.9	56.2	57.2	5.40
26.0	26.4	57.3	58.3	5.50
26.5	26.8	58.4	59.2	5.60
26.9	27.3	59.3	60.3	5.70
27.4	27.8	60.4	61.4	5.80
27.9	28.3	61.5	62.5	5.90
28.4	28.7	62.6	63.4	6.00
28.8	29.2	63.5	64.5	6.10
29.3	29.7	64.6	65.6	6.20
29.8	30.2	65.7	66.7	6.30
30.3	30.6	66.8	67.6	6.40
30.7	31.1	67.7	68.7	6.50
31.2	31.6	68.8	69.8	6.60
31.7	32.1	69.9	70.9	6.70
32.2	32.5	71.0	71.8	6.80
32.6	33.0	71.9	72.9	6.90
33.1	33.5	73.0	74.0	7.00
33.6	34.0	74.1	75.1	7.10
34.1	34.4	75.2	76.0	7.20

Somapacitan 15mg/1.5ml - Dose Level 0.21mg/kg				
34.5	34.9	76.1	77.1	7.30
Weight (kg)		Weight (lb)		
Start	End	Start	End	Dose
35.0	35.4	77.2	78.2	7.40
35.5	35.9	78.3	79.3	7.50
36.0	36.4	79.4	80.4	7.60
36.5	36.8	80.5	81.2	7.70
36.9	37.3	81.3	82.4	7.80
37.4	37.8	82.5	83.5	7.90
37.9	38.3	83.6	84.6	8.00
38.4	38.7	84.7	85.4	8.10
38.8	39.2	85.5	86.5	8.20
39.3	39.7	86.6	87.6	8.30
39.8	40.2	87.7	88.7	8.40
40.3	40.6	88.8	89.6	8.50
40.7	41.1	89.7	90.7	8.60
41.2	41.6	90.8	91.8	8.70
41.7	42.1	91.9	92.9	8.80
42.2	42.5	93.0	93.8	8.90
42.6	43.0	93.9	94.9	9.00
43.1	43.5	95.0	96.0	9.10
43.6	44.0	96.1	97.1	9.20
44.1	44.4	97.2	98.0	9.30
44.5	44.9	98.1	99.1	9.40
45.0	45.4	99.2	100.2	9.50
45.5	45.9	100.3	101.3	9.60
46.0	46.4	101.4	102.4	9.70
46.5	46.8	102.5	103.3	9.80
46.9	47.3	103.4	104.4	9.90
47.4	47.8	104.5	105.5	10.00
47.9	48.3	105.6	106.6	10.10
48.4	48.7	106.7	107.5	10.20
48.8	49.2	107.6	108.6	10.30
49.3	49.7	108.7	109.7	10.40
49.8	50.2	109.8	110.8	10.50
50.3	50.6	110.9	111.7	10.60
50.7	51.1	111.8	112.8	10.70
51.2	51.6	112.9	113.9	10.80

Somapacitan 15mg/1.5ml - Dose Level 0.21mg/kg				
51.7	52.1	114.0	115.0	10.90
Weight (kg)		Weight (lb)		
Start	End	Start	End	Dose
52.2	52.5	115.1	115.9	11.00
52.6	53.0	116.0	117.0	11.10
53.1	53.5	117.1	118.1	11.20
53.6	54.0	118.2	119.2	11.30
54.1	54.4	119.3	120.1	11.40
54.5	54.9	120.2	121.2	11.50
55.0	55.4	121.3	122.3	11.60
55.5	55.9	122.4	123.4	11.70
56.0	56.4	123.5	124.5	11.80
56.5	56.8	124.6	125.3	11.90
56.9	57.3	125.4	126.4	12.00
57.4	57.8	126.5	127.5	12.10
57.9	58.3	127.6	128.6	12.20
58.4	58.7	128.7	129.5	12.30
58.8	59.2	129.6	130.6	12.40
59.3	59.7	130.7	131.7	12.50
59.8	60.2	131.8	132.8	12.60
60.3	60.6	132.9	133.7	12.70
60.7	61.1	133.8	134.8	12.80
61.2	61.6	134.9	135.9	12.90
61.7	62.1	136.0	137.0	13.00
62.2	62.5	137.1	137.9	13.10
62.6	63.0	138.0	139.0	13.20
63.1	63.5	139.1	140.1	13.30
63.6	64.0	140.2	141.2	13.40
64.1	64.4	141.3	142.1	13.50
64.5	64.9	142.2	143.2	13.60
65.0	65.4	143.3	144.3	13.70
65.5	65.9	144.4	145.4	13.80
66.0	66.4	145.5	146.5	13.90
66.5	66.8	146.6	147.4	14.00
66.9	67.3	147.5	148.5	14.10
67.4	67.8	148.6	149.6	14.20
67.9	68.3	149.7	150.7	14.30
68.4	68.7	150.8	151.6	14.40

Somapacitan 15mg/1.5ml - Dose Level 0.21mg/kg				
68.8	69.2	151.7	152.7	14.50
Weight (kg)		Weight (lb)		
Start	End	Start	End	Dose
69.3	69.7	152.8	153.8	14.60
69.8	70.2	153.9	154.9	14.70
70.3	70.6	155.0	155.8	14.80
70.7	71.1	155.9	156.9	14.90
71.2	71.6	157.0	158.0	15.00
71.7	72.1	158.1	159.1	15.10
72.2	72.5	159.2	160.0	15.20
72.6	73.0	160.1	161.1	15.30
73.1	73.5	161.2	162.2	15.40
73.6	74.0	162.3	163.3	15.50
74.1	74.4	163.4	164.1	15.60
74.5	74.9	164.2	165.2	15.70
75.0	75.4	165.3	166.3	15.80
75.5	75.9	166.4	167.4	15.90
76.0	76.4	167.5	168.6	16.00
76.5	76.8	168.7	169.4	16.10
76.9	77.3	169.5	170.5	16.20
77.4	77.8	170.6	171.6	16.30
77.9	78.3	171.7	172.7	16.40
78.4	78.7	172.8	173.6	16.50
78.8	79.2	173.7	174.7	16.60
79.3	79.7	174.8	175.8	16.70
79.8	80.2	175.9	176.9	16.80
80.3	80.6	177.0	177.8	16.90
80.7	81.1	177.9	178.9	17.00
81.2	81.6	179.0	180.0	17.10
81.7	82.1	180.1	181.1	17.20
82.2	82.5	181.2	182.0	17.30
82.6	83.0	182.1	183.1	17.40
83.1	83.5	183.2	184.2	17.50
83.6	84.0	184.3	185.3	17.60
84.1	84.4	185.4	186.2	17.70
84.5	84.9	186.3	187.3	17.80
85.0	85.4	187.4	188.4	17.90
85.5	85.9	188.5	189.5	18.00

Somapacitan 15mg/1.5ml - Dose Level 0.21mg/kg				
86.0	86.4	189.6	190.6	18.10
Weight (kg)		Weight (lb)		
Start	End	Start	End	Dose
86.5	86.8	190.7	191.5	18.20
86.9	87.3	191.6	192.6	18.30
87.4	87.8	192.7	193.7	18.40
87.9	88.3	193.8	194.8	18.50
88.4	88.7	194.9	195.7	18.60
88.8	89.2	195.8	196.8	18.70
89.3	89.7	196.9	197.9	18.80
89.8	90.2	198.0	199.0	18.90
90.3	90.6	199.1	199.9	19.00
90.7	91.1	200.0	201.0	19.10
91.2	91.6	201.1	202.1	19.20
91.7	92.1	202.2	203.2	19.30
92.2	92.5	203.3	204.0	19.40
92.6	93.0	204.1	205.1	19.50
93.1	93.5	205.2	206.3	19.60
93.6	94.0	206.4	207.4	19.70
94.1	94.4	207.5	208.2	19.80
94.5	94.9	208.3	209.3	19.90
95.0	95.4	209.4	210.4	20.00
95.5	95.9	210.5	211.5	20.10
96.0	96.4	211.6	212.6	20.20
96.5	96.8	212.7	213.5	20.30
96.9	97.3	213.6	214.6	20.40
97.4	97.8	214.7	215.7	20.50
97.9	98.3	215.8	216.8	20.60
98.4	98.7	216.9	217.7	20.70
98.8	99.2	217.8	218.8	20.80
99.3	99.7	218.9	219.9	20.90
99.8	100.0	220.0	220.6	21.00

Table 10-10 Selection of somapacitan dose in mg in case of dose reduction to a dose level of 0.18mg/kg

Somapacitan 15mg/1.5ml - Dose Level 0.18mg/kg				
Weight (kg)		Weight (lb)		
Start	End	Start	End	Dose

Somapacitan 15mg/1.5ml - Dose Level 0.18mg/kg				
12.0	12.4	26.5	27.5	2.20
Weight (kg)		Weight (lb)		
Start	End	Start	End	Dose
12.5	13.0	27.6	28.8	2.30
13.1	13.5	28.9	29.9	2.40
13.6	14.1	30.0	31.2	2.50
14.2	14.6	31.3	32.3	2.60
14.7	15.2	32.4	33.6	2.70
15.3	15.8	33.7	35.0	2.80
15.9	16.3	35.1	36.1	2.90
16.4	16.9	36.2	37.4	3.00
17.0	17.4	37.5	38.5	3.10
17.5	18.0	38.6	39.8	3.20
18.1	18.5	39.9	40.9	3.30
18.6	19.1	41.0	42.2	3.40
19.2	19.6	42.3	43.3	3.50
19.7	20.2	43.4	44.7	3.60
20.3	20.8	44.8	46.0	3.70
20.9	21.3	46.1	47.1	3.80
21.4	21.9	47.2	48.4	3.90
22.0	22.4	48.5	49.5	4.00
22.5	23.0	49.6	50.8	4.10
23.1	23.5	50.9	51.9	4.20
23.6	24.1	52.0	53.3	4.30
24.2	24.6	53.4	54.4	4.40
24.7	25.2	54.5	55.7	4.50
25.3	25.8	55.8	57.0	4.60
25.9	26.3	57.1	58.1	4.70
26.4	26.9	58.2	59.4	4.80
27.0	27.4	59.5	60.5	4.90
27.5	28.0	60.6	61.8	5.00
28.1	28.5	61.9	63.0	5.10
28.6	29.1	63.1	64.3	5.20
29.2	29.6	64.4	65.4	5.30
29.7	30.2	65.5	66.7	5.40
30.3	30.8	66.8	68.0	5.50
30.9	31.3	68.1	69.1	5.60
31.4	31.9	69.2	70.4	5.70

Somapacitan 15mg/1.5ml - Dose Level 0.18mg/kg				
32.0	32.4	70.5	71.5	5.80
Weight (kg)		Weight (lb)		
Start	End	Start	End	Dose
32.5	33.0	71.6	72.9	5.90
33.1	33.5	73.0	74.0	6.00
33.6	34.1	74.1	75.3	6.10
34.2	34.6	75.4	76.4	6.20
34.7	35.2	76.5	77.7	6.30
35.3	35.8	77.8	79.0	6.40
35.9	36.3	79.1	80.1	6.50
36.4	36.9	80.2	81.5	6.60
37.0	37.4	81.6	82.6	6.70
37.5	38.0	82.7	83.9	6.80
38.1	38.5	84.0	85.0	6.90
38.6	39.1	85.1	86.3	7.00
39.2	39.6	86.4	87.4	7.10
39.7	40.2	87.5	88.7	7.20
40.3	40.8	88.8	90.1	7.30
40.9	41.3	90.2	91.2	7.40
41.4	41.9	91.3	92.5	7.50
42.0	42.4	92.6	93.6	7.60
42.5	43.0	93.7	94.9	7.70
43.1	43.5	95.0	96.0	7.80
43.6	44.1	96.1	97.3	7.90
44.2	44.6	97.4	98.4	8.00
44.7	45.2	98.5	99.8	8.10
45.3	45.8	99.9	101.1	8.20
45.9	46.3	101.2	102.2	8.30
46.4	46.9	102.3	103.5	8.40
47.0	47.4	103.6	104.6	8.50
47.5	48.0	104.7	105.9	8.60
48.1	48.5	106.0	107.0	8.70
48.6	49.1	107.1	108.4	8.80
49.2	49.6	108.5	109.5	8.90
49.7	50.2	109.6	110.8	9.00
50.3	50.8	110.9	112.1	9.10
50.9	51.3	112.2	113.2	9.20
51.4	51.9	113.3	114.5	9.30

Somapacitan 15mg/1.5ml - Dose Level 0.18mg/kg				
52.0	52.4	114.6	115.6	9.40
Weight (kg)		Weight (lb)		
Start	End	Start	End	Dose
52.5	53.0	115.7	117.0	9.50
53.1	53.5	117.1	118.1	9.60
53.6	54.1	118.2	119.4	9.70
54.2	54.6	119.5	120.5	9.80
54.7	55.2	120.6	121.8	9.90
55.3	55.8	121.9	123.1	10.00
55.9	56.3	123.2	124.2	10.10
56.4	56.9	124.3	125.6	10.20
57.0	57.4	125.7	126.7	10.30
57.5	58.0	126.8	128.0	10.40
58.1	58.5	128.1	129.1	10.50
58.6	59.1	129.2	130.4	10.60
59.2	59.6	130.5	131.5	10.70
59.7	60.2	131.6	132.8	10.80
60.3	60.8	132.9	134.2	10.90
60.9	61.3	134.3	135.3	11.00
61.4	61.9	135.4	136.6	11.10
62.0	62.4	136.7	137.7	11.20
62.5	63.0	137.8	139.0	11.30
63.1	63.5	139.1	140.1	11.40
63.6	64.1	140.2	141.4	11.50
64.2	64.6	141.5	142.5	11.60
64.7	65.2	142.6	143.9	11.70
65.3	65.8	144.0	145.2	11.80
65.9	66.3	145.3	146.3	11.90
66.4	66.9	146.4	147.6	12.00
67.0	67.4	147.7	148.7	12.10
67.5	68.0	148.8	150.0	12.20
68.1	68.5	150.1	151.1	12.30
68.6	69.1	151.2	152.5	12.40
69.2	69.6	152.6	153.6	12.50
69.7	70.2	153.7	154.9	12.60
70.3	70.8	155.0	156.2	12.70
70.9	71.3	156.3	157.3	12.80
71.4	71.9	157.4	158.6	12.90

Somapacitan 15mg/1.5ml - Dose Level 0.18mg/kg				
72.0	72.4	158.7	159.7	13.00
Weight (kg)		Weight (lb)		
Start	End	Start	End	Dose
72.5	73.0	159.8	161.1	13.10
73.1	73.5	161.2	162.2	13.20
73.6	74.1	162.3	163.5	13.30
74.2	74.6	163.6	164.6	13.40
74.7	75.2	164.7	165.9	13.50
75.3	75.8	166.0	167.2	13.60
75.9	76.3	167.3	168.3	13.70
76.4	76.9	168.4	169.7	13.80
77.0	77.4	169.8	170.8	13.90
77.5	78.0	170.9	172.1	14.00
78.1	78.5	172.2	173.2	14.10
78.6	79.1	173.3	174.5	14.20
79.2	79.6	174.6	175.6	14.30
79.7	80.2	175.7	176.9	14.40
80.3	80.8	177.0	178.3	14.50
80.9	81.3	178.4	179.4	14.60
81.4	81.9	179.5	180.7	14.70
82.0	82.4	180.8	181.8	14.80
82.5	83.0	181.9	183.1	14.90
83.1	83.5	183.2	184.2	15.00
83.6	84.1	184.3	185.5	15.10
84.2	84.6	185.6	186.6	15.20
84.7	85.2	186.7	188.0	15.30
85.3	85.8	188.1	189.3	15.40
85.9	86.3	189.4	190.4	15.50
86.4	86.9	190.5	191.7	15.60
87.0	87.4	191.8	192.8	15.70
87.5	88.0	192.9	194.1	15.80
88.1	88.5	194.2	195.2	15.90
88.6	89.1	195.3	196.6	16.00
89.2	89.6	196.7	197.7	16.10
89.7	90.2	197.8	199.0	16.20
90.3	90.8	199.1	200.3	16.30
90.9	91.3	200.4	201.4	16.40
91.4	91.9	201.5	202.7	16.50

Somapacitan 15mg/1.5ml - Dose Level 0.18mg/kg

92.0	92.4	202.8	203.8	16.60
Weight (kg)		Weight (lb)		
Start	End	Start	End	Dose
92.5	93.0	203.9	205.1	16.70
93.1	93.5	205.2	206.3	16.80
93.6	94.1	206.4	207.6	16.90
94.2	94.6	207.7	208.7	17.00
94.7	95.2	208.8	210.0	17.10
95.3	95.8	210.1	211.3	17.20
95.9	96.3	211.4	212.4	17.30
96.4	96.9	212.5	213.7	17.40
97.0	97.4	213.8	214.8	17.50
97.5	98.0	214.9	216.2	17.60
98.1	98.5	216.3	217.3	17.70
98.6	99.1	217.4	218.6	17.80
99.2	99.6	218.7	219.7	17.90
99.7	100.0	219.8	220.6	18.00

10.9 Appendix 9 Technical complaints: Definition and procedures for recording, evaluation, follow-up and reporting

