6.5.1 Dose reduction criteria

If adverse events (AEs) with a probable relationship to the trial product are severe but allow continuation in the study, as judged by the investigator, a dose reduction can be considered at the investigator's discretion. A reduction of the dose leading to a 25% reduction of the current exposure level is recommended (See [Table 6-2](#)). If the AE persists after the first dose reduction, a second dose reduction may be considered. If the AE is not resolved after two dose reductions the participant's treatment may be discontinued according to treatment discontinuation or withdrawal

criteria (see Section [7](#)). Treatment with a reduced dose should be for at least 4 weeks before dose can be resumed to the original planned dose at the investigator's discretion.

In the present study, dose will, furthermore, be reduced, if two consecutive IGF-I measurements confirmed by a re-test are above +3.0 SDS, if it is confirmed that the IGF-I sample is taken according to protocol. If IGF-I SDS exceeds +3.0 SDS at two consecutive visits the investigator will be contacted by Novo Nordisk and requested to reach out to the participant as soon as possible. The participant should be invited for a re-test within 4 weeks to confirm persistent IGF-I levels above +3.0 SDS. Blood samples for the confirmatory measurement of IGF-I should be collected at the end of the dosing interval (day 7 post-dose).

If IGF-I is still elevated above +3.0 SDS in the additional confirmatory measurement, dose reduction to a lower dose level will be required. Treatment with a reduced dose should be for at least 4 weeks before a subsequent IGF-I determination can result in further dose reduction. If the next scheduled visit is less than 4 weeks after the dose reduction was effectuated, the IGF-I result at that visit must NOT be used for evaluation of an additional dose reduction. At the next visit (or at an extra, unscheduled visit which complies with the 4 weeks minimum period), IGF-I will be re-tested.

Details about dose reduction are included below.

In the extension periods of the study, if the IGF-I level is below 1 SDS following dose reduction, the dose can be increased to the previous (higher) dose level.

First dose reduction

The first dose-reduction should be from 0.24 mg/kg/week to 0.21 mg/kg/week (See [Table 6-2](#)). This dose reduction step is expected to provide at least 25% reduction in somapacitan exposure considering the non-linear PK of somapacitan.

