
Second dose reduction

If, after first dose reduction, IGF-I exceeds +3.0 SDS at two (2) consecutive visits and is confirmed by re-test following the above described process, somapacitan dose should be reduced from 0.21 mg/kg/week to 0.18 mg/kg/week (See [Table 6-2](#)). This dose reduction step is expected to provide an additional 25% reduction in somapacitan exposure considering the non-linear PK of somapacitan.

Continuous persistently elevated IGF-I after two dose reductions

If, after second dose reduction, IGF-I exceeds +3.0 SDS at two (2) consecutive visits and is confirmed by re-test following the above-described process, the participant should be offered individual medical advice by the investigator.

In case of dose reduction, relevant dosing tables must be requested from Novo Nordisk.

Table 6-2 Dose reduction for somapacitan

Original dose (mg/kg/week)	Dose after first reduction (mg/kg/week)	Dose after second reduction (mg/kg/week)
0.24	0.21	0.18

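### The reduced-dose tables and split instruction in Appendix 8 are not aligned with the full-dose table on weight range and number of injections, and it is unclear which tables govern

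*Protocol*

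**What the plan says.** Protocol Section 6.5 sets the dose from body weight at each visit, makes the Appendix 8 table compulsory for finding it, and allows departures only under Section 6.5.1. Under Section 6.5.1, once IGF-I has been above +3.0 SDS at two consecutive visits and a re-test confirms it, "dose reduction to a lower dose level will be required". Table 6-2 gives the steps as 0.24, then 0.21, then 0.18 mg/kg/week. On where the reduced doses are found, Section 6.5.1 says: "In case of dose reduction, relevant dosing tables must be requested from Novo Nordisk".

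Appendix 8 (Section 10.8) then has two parts.

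- **Full dose.** "The dose table covers a body weight range from 9 to 125 kg". The split rule names no number: "A dose may be split into equal administrations in case the dose is higher than the pen can dispense for one administration". Table 10-8 has four injection columns. This part also says that the sponsor will provide tables for reduced doses.
- **Reduced dose** (under the heading on dose calculation). Sites are told to use the printed Tables 10-9 and 10-10. The split rule is "A dose may be split into two equal administrations in case the dose is higher than the pen can dispense for the administration". Both tables give a total dose only, with no injection columns, and their last rows end at 100.0 kg.

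**The concern.** A site that has to reduce the dose of a heavier participant needs three things from the appendix: a row for the weight, a way to divide the dose, and certainty about which table to use. Table 10-8 supplies the first two at full dose up to 125.0 kg. The reduced-dose part supplies neither across the same range, and three sentences in two sections disagree about the source. The sponsor has treated these weights as relevant: the history for protocol version 4.0 in Appendix 13 says that Table 10-8 was extended to guide dosing above 100 kg. The eligibility criteria set no upper weight limit, participants may enter at almost 18 years, and treatment can last up to 5 years.

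What is at stake is whether sites can carry out a required safety step in the same way from the document they hold. The estimands are not at stake. Section 3 counts dose reduction as part of the treatment condition for the primary estimand, and no analysis in the SAP depends on how an injection is divided.

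**Working it through.** **1. Reproduce the printed doses.** Dose = weight × level, rounded to 0.1 mg.

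| Table | Weight (kg) | Calculation | Printed (mg) |
|---|---|---|---|
| 10-9 | 76.4 | 76.4 × 0.21 = 16.044 | 16.0 |
| 10-9 | 76.5 | 76.5 × 0.21 = 16.065 | 16.1 |
| 10-9 | 100.0 | 100.0 × 0.21 = 21.0 | 21.0 |
| 10-10 | 89.1 | 89.1 × 0.18 = 16.038 | 16.0 |
| 10-10 | 89.2 | 89.2 × 0.18 = 16.056 | 16.1 |
| 10-10 | 100.0 | 100.0 × 0.18 = 18.0 | 18.0 |

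Seventeen boundary rows were checked across the three tables. Every end weight reproduces. Four start weights (100.2 kg at 0.24; 44.7, 88.6 and 99.7 kg at 0.18) round to 0.1 mg below the print. This is a row-edge effect that does not move the thresholds used here.

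**2. Infer the most that one injection carries.** The documents do not state the pen's maximum. Table 10-8 goes from one injection ("33.2 33.5 73.2 74.0 8.0 8.0 0.0 0.0 0.0") to two ("33.6 33.9 74.1 74.9 8.1 4.1 4.0 0.0 0.0") just above 8.0 mg, to three just above 16.0 mg ("66.9 67.2 147.5 148.3 16.1 5.4 5.4 5.3 0.0"), and to four just above 24.0 mg. Rounding dose ÷ 8.0 up to a whole number gives the printed number of injections at each of these boundaries: 8.0 → 1, 8.1 → 2, 16.0 → 2, 16.1 → 3, 24.0 → 3, 24.1 → 4, 30.0 → 4. A maximum of 8.0 mg fits the table, but it remains an assumption.

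**3. Apply the two-injection rule under that assumption.** 2 × 8.0 = 16.0 mg.

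- Table 10-9: exceeded from 76.5 kg to the end of the table, 50 dose rows (16.1 to 21.0 mg). Half-doses run from 16.1 ÷ 2 = 8.05 mg to 21.0 ÷ 2 = 10.5 mg.
- Table 10-10: exceeded from 89.2 kg, 20 dose rows (16.1 to 18.0 mg). Half-doses run from 8.05 mg to 18.0 ÷ 2 = 9.0 mg.
- For contrast, at 76.5 kg Table 10-8 prints the full dose of 18.4 mg as 6.1 + 6.1 + 6.2.

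**4. Vary the assumption.** The maximum cannot be below 8.0 mg, because Table 10-8 prints single injections of 8.0 mg. At 9.0 mg, two injections give 18.0 mg: Table 10-10 has no conflict, and Table 10-9 has one from 86.0 kg (18.1 mg). At 10.5 mg or more, no printed row conflicts.

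**5. Compare weight ranges.** Table 10-8 ends at 125.0 kg and both reduced tables end at 100.0 kg. Weights from 100.1 to 125.0 kg have a full-dose row and no reduced-dose row. This does not depend on step 2.

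**6. Compare the stated sources.** Section 6.5.1 says that sites request the tables, the full-dose part of Appendix 8 says that the sponsor provides them, and the reduced-dose part says to use those printed. No sentence ranks these.

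**The case against.** A reader might infer that some required reductions cannot be given at all. The documents do not support that. Sponsor-supplied tables are a written route, and under Section 6.5.1 the sponsor already contacts the investigator after two IGF-I values above +3.0 SDS, so such tables could cover the missing weights and splits. The split sentence is permissive, although it describes no other division for reduced doses. Between 76.5 and 100.0 kg the total dose is printed and only its division is in doubt. The pen's directions for use, which might settle the maximum, are not among the documents. All of this stands, and it limits the point to the appendix as written.

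Two further inferences fail. One is that doses such as 8.1 mg cannot be divided because they do not halve in 0.1 mg steps. Table 10-8 prints 4.1 + 4.0 under its own rule of equal parts, so near-equal parts have a precedent. The other is that the mismatch would feed the primary endpoint through medication errors. The examples in Section 10.3.3 are a wrong drug or device, a wrong route, and an accidental overdose judged likely to have clinical consequences. The same total given in more injections matches none of them.

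Reach is also small. At most 50 children are to be enrolled. For a GH-naïve boy at the −2 SDS limit in the last row of Table 10-7 (161.6 cm), 76.5 kg is a BMI of 76.5 ÷ 1.616² ≈ 29 and 100 kg is about 38. Participants who are not GH-naïve have no height limit, so heavier cases are possible. The mandatory reduction also requires confirmed high IGF-I.

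**Conclusion.** The misalignment is real and minor. Two parts rest on the text alone: neither reduced-dose table has a row above 100.0 kg although the full-dose table reaches 125.0 kg, and the protocol does not settle whether printed or sponsor-supplied tables govern. One part is conditional: with a pen maximum of 8.0 mg, the two-injection instruction falls short of the printed dose from 76.5 kg at 0.21 mg/kg and from 89.2 kg at 0.18 mg/kg. The condition is well supported by the pattern in Table 10-8 but is not stated anywhere. Few participants are likely to be affected, and no endpoint or analysis is shown to be. The reason to correct it is that the reduction is mandatory and the appendix is the document that sites must use.

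**What to change.** The sponsor should reconcile Tables 10-9 and 10-10 and the reduced-dose split sentence with Table 10-8 on three items: weight range, number of injections and amount per injection. Stating the pen's maximum per injection in Appendix 8 would remove the need to infer it. The three sentences on the source of reduced-dose tables, one in Section 6.5.1 and two in Appendix 8, should agree on which tables apply. What the rows and splits should contain is for the sponsor to decide. The cost is an edit to two tables and a few sentences; the SAP, data collection and analyses do not change.
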